6.2.4 Medical History

During the screening process patient demographic and medical information acquired from the patient or the patient's medical chart, including previous medical history, medications, history of clinically significant abnormalities of all body systems; concurrent diseases; relevant past medical history.

The relevant information will be recorded in the case report forms for all patients participating in this study.

Date issued:
05 Dec2018

SUBJECT: Functionality and Accuracy of the smART System in Real-Life ICU Settings

Number: CLT3_SY_P001

Revision 08

Page 22 of 38

6.2.5 Physical Examination

During the screening process all patients will undergo a physical examination by an authorized physician. The physical examination will include diagnosis and documentation of any significant abnormalities or diseases relevant to the placement and utilization of the feeding tube.

6.2.6 Study Schedule

Procedures	Screening/ enrollment	Medical Device Placement	Ongoing use	Termination
Day	1	1	Up to 7	2.3 up to 7
Informed Consent	+			
Eligibility Criteria	+			
Physical Exam	+			
Pregnancy test (if applicable)	+			
Vital Signs		+	+	+
Lab Data				+
Medical Device Administration		+	+	
GRV Measurements			+ as needed and according to procedures	
Aspiration of gastric contents recording			+	
Pepsin Test			+ Collected every 8 hrs. during routine tracheal suction	
Adverse Events	+	+	+	+
Concomitant Medication		+	+	+
Patient positioning		+	+	

SUBJECT: Functionality and Accuracy of the smART System in Real-Life ICU Settings

Number: CLT3_SY_P001

Revision 08

Page 23 of 38

Information regarding nutritional supplement administration		+	+	
Patient responses		+	+	
Endoscopy (performed on up to 7 subjects)			+ if blood residue is visible on balloon following tube removal (within 5hrs. of tube removal)	+ On subjects enrolled for a duration of more than 5 days (within 5hrs. of tube removal)

6.2.7 Study End

Study participation for each patient will end in the following cases:

- Subject has reached the maximum 7-day duration of participation
- Subject is being transferred to a different ward/facility
- Patient withdrew consent
- Related adverse event
- Death

6.2.8 Deviations from study protocol

Any deviations from the study protocol should be reported to the sponsor and documented on study deviation forms.

6.2.9 Investigative Center Selection Criteria

The investigative site will meet the following selection criteria prior to inclusion in this study:

- Clinical research study experience and resources that demonstrate good compliance with study requirements and timely, complete documentation of subject data.
- Sufficient subject volume to meet enrollment timeframe.

6.2.10 Replacement of Feeding bag

During the procedure, feeding bag should be replaced as needed.

Date issued:
05 Dec2018

SUBJECT: Functionality and Accuracy of the smART System in Real-Life ICU Settings

Number: CLT3_SY_P001

Revision 08

Page 24 of 38

6.2.11 Tracheal suction

During the study, tracheal suctioning will be performed in accordance with hospital procedures. Once every eight hours a sample of tracheal suction of at least 2 cc, will be instilled in a LUKI trap and stored in a freezer to later be shipped to a lab for analysis.

6.2.12 Replacement of Subjects

All subjects that participate in the study for a duration of 2.3 days (56 hrs.±2) up to 7 days (168 hrs. ±2), at termination will be considered as complete. In case of premature withdrawal of subjects from the study (i.e., withdrew prior to participation of 56 hrs.±2), additional subjects may be enrolled to reach the target number following a discussion between the Principal Investigator and the Sponsor. New subjects will undergo the same procedures and assessments as specified in the protocol.

A patient will be considered officially enrolled in the study once signing ICF obtained.

6.2.13 Subject Identification and Confidentiality

A subject's case number will be composed of a two-digit number that represents the sequential serial number of study enrollment at the site and initials.

All reports and communications relating to study subjects will identify the subject only by his case number, initials and unique identification code. The subject identification will be kept confidential at the investigational site according to the local SOPs.

6.2.14 Subject Withdrawal or Discontinuation

Each subject (or delegate) will be informed of his/her right to withdraw from the study at any time and for any reason.

The Investigator may withdraw a subject from the study at any time if he considers that remaining in the study compromises the subject's health.

Additional criteria for withdrawal:

- The insertion of the feeding tube has failed after **2** attempts in each nostril

The reasons for any subject withdrawal will be recorded on the study completion form of the CRF. The investigator will inform the Sponsor in writing of the subject's early withdrawal for any reason.

If withdrawal is caused by an adverse event that the investigator considers may be related to the device, it will be reported to the IRB and to the Sponsor.

6.2.15 Replacement of Feeding tube

During the feeding, feeding tube replacement is allowed in the following cases:

- Feeding tube blockage
- Visual related
- Alarm or warning related to feeding tube according to the user manual.
- The medical staff decision to stop feeding and remove the feeding tube due to unrelated medical reasons.
- Other medical reasons unrelated to feeding process.
- Routine procedures

In the above cases, after replacing the feeding tube with a new one, the patient will continue the study to the remaining time of the study duration. Visual inspection of feeding tube should be performed as indicated in section 6.2.3 Study Specific Procedures.

7 Adverse Events, Adverse Device Effects and Device Deficiencies

7.1 Definitions of Adverse Device Effects and Adverse Events

7.1.1 Adverse Device Effect (ADE)

An "Adverse Device Effect" is an adverse event related to the use of an investigational medical device.

NOTE 1- This includes any adverse event resulting from insufficiencies or inadequacies in the instructions for use, the deployment, the implantation, the installation, the operation, or any malfunction of the investigational medical device.

NOTE 2- This includes any event that is a result of a use error or intentional misuse.

"Adverse Events" are defined as any untoward medical occurrence, unintended disease or injury or any untoward clinical signs (including an abnormal laboratory finding) in subjects, users or other persons whether or not related to the investigational medical device.

NOTE 1: This includes events related to the investigational device or the comparator.

NOTE 2: This includes events related to the procedures involved (any procedure in the clinical investigation plan).

NOTE 3: For users or other persons this is restricted to events related to the investigational medical device.

SUBJECT: Functionality and Accuracy of the smART System in Real-Life ICU Settings

Number: CLT3_SY_P001

Revision 08

Page 26 of 38

All adverse events will be graded for severity as follows:

Mild: Sign or symptom, usually transient, requiring no special treatment and generally not interfering with usual activities.

Moderate: Sign or symptom, which may be ameliorated by simple therapeutic measures; yet, may interfere with usual activity.

Severe: Sign or symptom that are intense or debilitating and that interfere with usual activities. Recovery is usually aided by therapeutic measures.

The relationship of the adverse event to the treatments or procedures is defined as follows:

Probably related: Follows a reasonable temporal sequence from study device delivery/retrieval, and cannot be reasonably explained by known characteristics of the subject's clinical data or the surgical procedure applied.

Possible related: Follows a reasonable temporal sequence from study device delivery/retrieval but could have been produced by the subject's clinical state or by the surgical procedures regardless of the study device.

Not related: No relationship to study device activation is perceived.

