4.1 Primary Endpoints

Functionality

- the system is able to accurately guide the user to ensure correct initial placement (verified by X-ray)
- the system is able to detect tube movement/displacement during ongoing use (verified by markings on the tube)
- the system automatically stops feeding when tube displacement is detected
- the system automatically stops feeding when reflux is detected
- the system automatically inflates the balloon when a reflux episode is detected

Safety

- occurrence of device related adverse events

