Every smART feeding tube removal should be documented in the CRF and the relevant device information (i.e., serial number) should be recorded. If a smART tube is replaced by a different smART tube, the reason for replacement should be documented and the serial number of the new device being used should be recorded.

- **Endoscopy/esophageal imaging**

One third of the study population will undergo endoscopy to evaluate potential trauma to the esophagus as a result of balloon inflation.

Endoscopy will be indicated for those patients who:

- Have been enrolled in the study for a duration of more than 5 days;

Or,

- Had noticeable blood residue on the feeding tube following tube removal.

PATIENT SAFETY THROUGH TECHNOLOGY

Date issued:
05 Dec2018

SUBJECT: Functionality and Accuracy of the smART System in Real-Life ICU Settings

Number: CLT3_SY_P001

Revision 08

Page 21 of 38

If by the time patient number 13 is enrolled, no endoscopies have been performed, the remaining 7 patients will undergo endoscopy for local evaluation of trauma in the area of the esophagus where the balloon is inflated.

Every effort will be made to obtain at least 7 patients with endoscopic assessment.

Procedure - Following tube removal (within 5 hrs.) patients eligible for endoscopy (based on the above definition) shall undergo an endoscopic procedure to evaluate the balloon inflation site. Specifically, any noticeable trauma to the esophagus shall be recorded in the relevant CRF pages (e.g., adverse event form).

- Aspiration of gastric contents recording

Local site procedure for tracheal suction should be followed as needed and according to hospital procedures. Once every eight hours a sample of at least 2 cc should be instilled in a LUKI trap. The sample should be appropriately labeled and recorded by the medical staff in the bed side CRF log (Pepsin Test). The sample should be kept frozen until transportation to the lab.

- Used/Unused Devices

Used devices will be returned back to the bag in which they were provided in by the sponsor. All the bags will be collected by the sponsor, and accountability logs will be updated accordingly.

All unused devices and study materials will be collected by the sponsor at the end of the study.

- Staff Questionnaires:

At the end of the study, staff will be required to complete a usability questionnaire assessing the ease of use and functionality of the device (refer to Appendix 2).

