7.3 Adverse Event Reporting

All adverse events will be recorded on the adverse events page of the CRF.

Severity and relationship to study device will be assigned by the investigator as described in the section above.

Adverse events will be recorded after the subject (or delegate) has signed the informed consent and throughout the study including the follow-up termination visit. Adverse events should be reviewed and updated at each subsequent visit and during any phone contact with the subject.

Date issued:
05 Dec2018

SUBJECT: Functionality and Accuracy of the smART System in Real-Life ICU Settings

Number: CLT3_SY_P001 Revision 08

Page 28 of 38

Any SAE, whether deemed device-related or not, must be reported to the site Ethics Committee and to the sponsor's Safety Medical Officer by telephone and by Fax, as soon as possible after the investigator has become aware of its occurrence even if not all the information is available at the time of initial contact:

Safety Medical Officer contact information:

[name]

[contact]

Email: [contact]

The investigator must complete a SAE Form, and send it, via fax, to the Sponsor within 24 hours of becoming aware of the event. Accompanying documentation, such as copies of hospital case reports, autopsy report, and other documents when applicable, should be sent as soon as they are available.

The site's Ethics Committee must also be duly notified and dealt with, according to the local and federal regulations.

Subjects who have had an SAE must be followed clinically until all parameters (including laboratory) either have returned to normal or are stabilized.

8 Monitoring Plan

[figure not shown]
Monitoring functions shall be performed in compliance with Good Clinical Practices, EN ISO 14155:2011, as outlined in 21CFR§821.43(d) and 21CFR§812.46, and according to any other local regulations.

ART Healthcare will appoint a Clinical Monitor for this study. The Clinical Monitor should be qualified by training and experience to oversee the conduct of the study. The Clinical Monitor's responsibilities include maintaining regular contact with the investigational site, through telephone contact and on-site visits, to ensure that: 1) the study protocol is followed; 2) that complete, timely, and accurate data are gathered; 3) that problems with inconsistent and incomplete data are addressed; and 4) that complications and Unanticipated Adverse Device Effects are reported to the Sponsor.

9 Statistical considerations

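### The adverse-event causality scale rates only the device, so an injury from the protocol's own endoscopy cannot be labelled as such and may be rated as possibly device-related

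*Combined protocol and SAP*

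**What the plan says.** - **What counts as an adverse event.** NOTE 2 to the definition in section 7.1.1 brings in harm from study procedures: "This includes events related to the procedures involved (any procedure in the clinical investigation plan".
- **What the scale says it rates.** The same section opens the scale with "The relationship of the adverse event to the treatments or procedures is defined as follows".
- **What the levels rate.** The top level begins "Probably related: Follows a reasonable temporal sequence from study device delivery/retrieval, and cannot be reasonably explained by known characteristics". The middle level has the same time anchor and covers events that "could have been produced by the subject's clinical state or by the surgical procedures regardless of the study device". The bottom level reads "Not related: No relationship to study device activation is perceived".
- **What the investigator assigns.** Section 7.3: "Severity and relationship to study device will be assigned by the investigator as described in the section above".
- **The added procedure.** Section 6.2.3 sends one third of the population to endoscopy, within 5 hours of tube removal, to look for esophageal trauma from balloon inflation. The indications are more than 5 days in the study or blood on the removed tube. If no endoscopy has been done by patient 13, "the remaining 7 patients will undergo endoscopy for local evaluation of trauma in the area of the esophagus". Any trauma seen goes on CRF pages such as the adverse event form.
- **The safety endpoint.** Section 4.1 has one: "occurrence of device related adverse events".

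**The concern.** The protocol counts procedure-related harm as an adverse event and announces a scale that covers procedures, then provides no way to rate a procedure as the cause. Procedures enter the scale only as a rival explanation that weakens the link to the device, and only as surgical procedures, although the protocol describes no study surgery.

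This matters here because endoscopy shares both site and time window with the device effect under study. It inspects the part of the esophagus where the balloon inflates, shortly after the tube comes out. Trauma caused by the scope could be taken for the balloon trauma that the endoscopy is looking for. Two things are at stake: how cleanly events are attributed in the only safety endpoint, and whether harm that exists only because of the study can be seen as such.

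**Working it through.** **1. The plan's own figure.** One third of 20 subjects is 20/3 = 6.67, rounded up to 7. The patient-13 fallback gives 20 − 13 = 7. The figure of 7 reproduces, and 7/20 = 35%. It is a target: section 6.2.3 aims for at least 7, while the schedule in section 6.2.6 says up to 7.

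**2. The scale, level by level.**

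| Element | Rated against | Role of procedures |
|---|---|---|
| Lead-in, 7.1.1 | Treatments or procedures | Announced as something to be rated |
| *Probably related* | Device delivery or retrieval | Rival cause (surgical) |
| *Possible related* | Device delivery or retrieval | Rival cause (surgical) |
| *Not related* | Device activation | None |
| Instruction, 7.3 | Study device | None |

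No other section supplies a procedure rating. The list of anticipated events in section 7.1.2 covers tube insertion, tube presence and feeding, but not endoscopy.

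**3. Trace one scope injury through the scale.** It occurs at or after an endoscopy done within 5 hours of tube removal, so it can be read as following device retrieval in a reasonable time sequence. Another cause is available, so *Possible related* fits its wording if endoscopy is accepted as a procedure of the kind meant. If the investigator sees no link to the device, *Not related* fits. Neither choice records that endoscopy was the cause.

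The sequence can be longer. Section 6.2.6 also places endoscopy for visible blood under ongoing use, and section 6.2.15 lets a subject continue with a new tube. One device-only rating would then cover removal, endoscopy and reinsertion.

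**4. Size of one such event.** Assumptions: a subject-level rate, 20 subjects, no true device event, one endoscopy-caused event, and exact (Clopper-Pearson) 95% intervals.

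| How the event is handled | Rate | 95% CI |
|---|---|---|
| *Possible related*, counted as device-related | 1/20 = 5.0% | 0.1% to 24.9% |
| *Not related* | 0/20 = 0% | 0% to 16.8% |
| Separate procedure rating: procedure line | 1/7 = 14.3% | 0.4% to 57.9% |
| Separate procedure rating: device line, if judged not due to the device | 0/20 = 0% | 0% to 16.8% |

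**5. How likely is at least one event?** The documents give no endoscopy complication rate. For an assumed per-procedure event rate p, the chance of at least one event in 7 independent endoscopies is 1 − (1 − p)^7:

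| Assumed p | Chance of at least one |
|---|---|
| 1% | 6.8% |
| 5% | 30.2% |
| 10% | 52.2% |
| 20% | 79.0% |

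These show the range only; they do not predict what will happen.

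**The case against.** A reader might infer that the primary safety result is wrong whichever way a scope injury is rated, and that study-caused harm is lost. The documents do not support this.

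- **Rated *Not related*, the endpoint is right.** Section 4.1 counts device-related events, and a scope injury is not one. It would stay outside that endpoint after the fix too.
- **The harm is still captured.** Under section 7.3 every adverse event goes on the CRF page, and every serious event is reported whether or not it is thought device-related. Section 9.2 summarises categorical data by frequency and percentage. What is missing is the label and a tally by procedure.
- **Inflation is conditional.** It needs *Possible related* to count as device-related, and the protocol does not say which levels count. It also needs the investigator to choose that level when *Not related* is open for an event recognised as caused by the scope.
- **Some ambiguity would remain.** For a truly unclear event, *Possible related* is a cautious rating, and a second rating does not settle the device question.
- **Exposure is uncertain.** The fallback applies only if no endoscopy has been done by patient 13; otherwise endoscopy depends on length of stay or blood on the tube. The study is descriptive with no stated safety threshold, so no prespecified decision turns on one event.

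All of this stands and limits the point. None of it supplies the procedure rating that section 7.1.1 announces, and neither serious-event reporting nor the CRF page, as described, separates the two causes.

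**Conclusion.** The scale does not do what its lead-in says. An endoscopy-caused event has no category of its own and can literally be rated *Possible related* to device retrieval. If that level enters the safety endpoint, one such event adds 5 percentage points (0/20 to 1/20) and raises the upper 95% limit from 16.8% to 24.9%. If the event is rated *Not related*, the device endpoint is unaffected and only its identification as procedure harm is lost. The inconsistency in wording rests on the text alone; the size rests on the assumptions in the working and on an endoscopy event rate that the documents do not give. This is a cheap improvement in attribution and does not show that the safety result will be wrong.

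**What to change.** - In sections 7.1.1 and 7.3, have the investigator rate each adverse event twice: relationship to the device, and relationship to a protocol-required procedure (endoscopy). Record whether onset was before or after endoscopy.
- Replace the references to surgical procedures with the procedures this study uses.
- State which levels of the device scale enter the section 4.1 safety endpoint.
- Keep that endpoint as device-related events, and add one table line for procedure-related events with endoscoped subjects as denominator.
- Reconcile the number of endoscopies in section 6.2.3 (at least 7) with section 6.2.6 (up to 7), since it sets that denominator.

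The cost is a minor CRF change, one table line and one more judgement per event for the investigator. No visit or procedure is added. The ratings are best made when the event occurs, so the change should be in place before enrolment.

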7.1.2 Anticipated Adverse Events

Anticipated adverse events associated with the insertion and presence of feeding tubes include:

- Inconvenient sensation in the neck or chest during or after insertion of the feeding tube and during feeding.
- Nasal bleeding during insertion attempt of the tube.
- Difficulty in breathing, coughing and chest pain due to insertion of the tube, mistakenly, into the trachea.
- Difficulty in swallowing due to the presence of the tube.
- Nausea and vomiting

Anticipated adverse events associated with feeding are:

- Abdominal discomfort and pain
- Abdominal bloating
- Diarrhea

7.2 Definitions of Serious Adverse Device Effect and Serious Adverse Event

SUBJECT: Functionality and Accuracy of the smART System in Real-Life ICU Settings

Number: CLT3_SY_P001

Revision 08

Page 27 of 38

7.2.1 Serious Adverse Device Effect (SADE)

A "Serious Adverse Device Effect" is an adverse device effect that has resulted in any of the consequences characteristic of a serious adverse event.

7.2.2 Serious Adverse Event (SAE)

A "serious Adverse Event is an adverse event that:

- a) led to a death,
- b) led to a serious deterioration in health that either:
 - 1) resulted in a life-threatening illness or injury, or
 - 2) resulted in a permanent impairment of a body structure or a body function, or
 - 3) required in-patient hospitalization or prolongation of existing hospitalization, or
 - 4) resulted in medical or surgical intervention to prevent life threatening illness or injury or permanent impairment to a body structure or a body function.
- c) led to fetal distress, fetal death or a congenital abnormality or birth defect.

NOTE 1: This includes device deficiencies that might have led to a serious adverse event if a) suitable action had not been taken or b) intervention had not been made or c) if circumstances had been less fortunate. These are handled under the SAE reporting system.

NOTE 2: A planned hospitalization for pre-existing condition, or a procedure required by the Clinical Investigation Plan, without a serious deterioration in health, is not considered to be a serious adverse event.

